#### **Follow-up Period:**

All subjects will return to the research site for a Follow-up visit (Visit 3 for cohort 1 and Visit 7 for cohorts 2-4), for medical assessment and collection of blood samples. The Follow-up visit will take place approximately 4 weeks (28 days ± 3 days) after the last dosing of each subject.

#### **3.3. Safety Review Committee**

For this study, a SRC has been assembled. After completion of cohort 1 and cohort 2 and the interim data analysis, the SRC is responsible for 1) providing recommendations on the dose escalation from 100 ng to 200 ng in cohort 4 based on the safety data collected up to and including cohort 3 Visit 5 and cohort 4 Visit 4, i.e. prior to cohort 4 Visit 5, where the administration of 200 ng dose is planned; 2) on continuation of dosing of cohort 3 to Visit 6; 3) on continuation or termination of the study; 4) on possible suspension or modification of dosing based on the study's stopping criteria (see Section 9); 5) on the appropriateness of the safety measures and the possible need for alterations. If needed, the study will be halted until appropriate measures have been taken to amend the study protocol and until all relevant approvals have been received to continue the study.

Additional SRC meetings will be held, as needed; additional meetings will be triggered by safety observations as described in Section 9.

The SRC includes members with experience in the conduct and risk assessment/management of clinical trials and ethical aspects. The SRC is comprised of the Principal Investigator, the Sponsor's Medical Monitor, representative(s) of the Sponsor and a qualified biostatistician.

Detailed instructions for SRC meetings and its decision-making process are described in a separate document called "SRC Instructions". The study data will be reviewed blinded. However, if it is deemed necessary for ascertaining the safety of the study subjects, the review may also be unblinded.

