## APPENDICES

Appendix 1. World Allergy Organisation Subcutaneous Immunotherapy Systemic Reaction Grading System

Appendix 2. Action Plan for Severe Allergic Reactions

## SYNOPSIS

Name of the Sponsor/Company:
Desentum Oy
Name of the finished product:
DM-101 Drug Product
Name of the active ingredient:
DM-101
Study code:
DM-101-C-001, EudraCT No: 2019-001936-67
Study title:
A randomized, double-blinded, placebo-controlled, dose escalation study to evaluate the safety and tolerability of subcutaneous immunotherapy with DM-101 in adults with birch pollen allergy
Investigators and study centres:
Principal Investigator, Clinical Research Services Turku - CRST Oy, Finland
Development phase:
Objectives:
Primary Objective: To evaluate the safety and tolerability of s.c. administration of DM-101 in adult subjects with birch pollen allergy.
Secondary Objective: To determine the proportion of adult subjects who reach the pre-defined maximum admissible s.c. DM-101 dose in each dosing group.
Exploratory Objective: To evaluate the possible effects of repeated s.c. DM-101 dosing on immunological biomarkers in adult subjects with birch pollen allergy.
Methodology:
The study is a randomized, double-blind, placebo-controlled, parallel group study to evaluate the safety and tolerability of DM-101 s.c. administration in subjects with birch pollen allergic rhino-conjunctivitis. The study is planned to be conducted outside of the birch pollen season in Finland.
The study will include up to 4 cohorts of participants. In each cohort, subjects are randomly allocated to receive s.c. doses of DM-101 or placebo. Cohort 1 includes a single dose administration. Cohorts 2 to 4 include escalating, repeat dose administration.
The study starts with cohort 1 and sequentially proceeds to cohorts 2, 3 and 4. Dose escalation will be initiated only upon satisfactory review of all available safety data from previous dose levels and favourable recommendation from the study's Safety Review Committee.

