### **Revised dose selection rationale for Cohorts 3 and 4**

Based on the safety findings from the initially conducted cohorts of this FIH trial and Desentum's latest laboratory data on the amount of biologically active Bet v 1 in commercially available birch pollen s.c. AIT products, it is considered important to continue this study with a DM-101 dosing scheme that carries low risk of induction of serious allergic reactions. To this end, the study design has been amended to include only 2 additional cohorts (cohorts 3 and 4) where DM-101 will be administered following a very slowly escalating repeat dose regimen, with doses starting from 30 ng, up to a maximum

of 300 ng. The rapid dose escalation over 2 consecutive days (Visit 2, Day 1 and 2) included in the original study protocol (version 1.1) has been omitted. Instead, a slow dose escalation that will take place over 5 bi-weekly dosing visits is proposed.

Dosing in both cohorts, 3 and 4, will start with administration of a single s.c. injection of placebo or 30 ng of DM-101 on Visit 2, followed by a single s.c. injection of placebo or 50 ng of DM-101 2 weeks later (Visit 3). Subsequently, in cohort 3 dosing will continue with single administration of placebo or 100 ng DM-101 on each of the Visits 4 to 6. In cohort 4, Visits 4 to 6 will include s.c. injections of placebo or increasing doses of DM-101 corresponding respectively to 100, 200 and 300 ng (Table 8). The doses of 200 ng and 300 ng will be administered as 2 and 3 s.c. injections of 100 ng respectively, with at least 30 min intervals between injections.

The starting dose of 30 ng has been selected because it was found to be safe and well-tolerated by the subjects who completed cohort 1 of this study. The subsequent 2nd dose of 50 ng and 3rd dose of 100 ng have been selected as modest steps of dose escalation in order to maximise safety. The 100 ng dose level has already been tested as the starting dose of the 4 subjects who received cohort 2 active treatment in this study; in these subjects, 100 ng DM-101 was not associated with the development of significant TEAEs or systemic allergic reactions. In cohort 3, 100 ng is the maximal planned dose that will be administered on subsequent visits until the end of the treatment phase. If this dosing scheme is well tolerated by the cohort 3 subjects, further dose escalation above 100 ng will be attempted in cohort 4 at Visit 4 (200 ng) and at Visit 5 (300 ng).

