Two-week intervals between doses are considered to be long enough for the intended immunological adaptation to develop, to allow dose escalation during the treatment period. This dosing interval was also used in the nonclinical toxicology evaluation of DM-101.

Cohort 4 will not be initiated until cohort 3 Visit 2 has been completed. Dose escalation to doses above 100 ng in cohort 4 will only take place if the review of the collected safety and tolerability data from Visit 5 of cohort 3 is favourable (see Section 3). Repeated dosing and dose escalation within these cohorts will also take place only if safety allows it and the study's dosing discontinuation or adjustment criteria (see Section 9) have not been met.

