#### **1.4. Revised Risk Benefit Assessment for Cohorts 3 and 4 – Protocol version 2.0**

Based on the outcomes of an interim analysis of the data collected from the subjects who participated in the first 2 cohorts of the study prior to the temporary halt due to the Covid-19 pandemic, the dose levels and dosing schemes for the subsequent dose cohorts have been revised for version 2.0 of the protocol.

Desentum has reassessed this FIH study for any risks that may be posed to the subjects. Only 2 new cohorts (cohorts 3 and 4), of similar size and composition as the originally planned 4 additional cohorts (cohorts 3-6), will be included with doses and dose escalation schemes substantially modified. The dose escalation schemes in cohorts 3 and 4 will provide information about the safety of repeated dosing on a bi-weekly basis, as well as on the development of desired immunological responses, both regarded as essential information for planning of phase II dose finding studies where the preliminary efficacy of DM-101 will be studied.

Based on the interim results from the cohort 1 and 2 subjects, transient, mild injection site reactions may occur with the doses selected for cohorts 3 and 4, but major safety risks are not anticipated. Systemic allergic reactions were reported in cohort 2, but none was reported following injection of the dose of 100 ng. Administration of doses above 100 ng per s.c. injection are not planned in the amended dosing regimen. It is acknowledged that s.c. AIT is associated with a low risk of reversible, systemic allergic reactions, mostly occurring within an hour following treatment administration (Kannan, 2013; James, 2017; Nurmatov, 2017). The use of standardized allergen extract products and rigorous practices of surveillance have made the risk for life-threatening reactions extremely small (Makatsori, 2014; Caminati, 2015). Nevertheless, the study involves risks and the potential development of local and systemic allergic reactions after dosing with DM-101 will be thoroughly monitored.

Specific risk management measures include the following:

- Only subjects in good general health and with no previous history of anaphylaxis, moderate to severe or uncontrolled asthma, or immunologic or other major disorders will participate in this study (see Inclusion/Exclusion Criteria, Section 4.2).

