### 3. STUDY DESIGN

#### 3.1. Overview

This will be a randomized, double blind, placebo-controlled, parallel group study to evaluate the safety and tolerability of s.c. administration of DM-101 in subjects with birch pollen-evoked allergic rhinoconjunctivitis. The study will be conducted outside of the birch pollen season in Finland.

The study will include up to 4 cohorts of participants. In each cohort, subjects will be randomly allocated to receive s.c. doses of DM-101 or placebo. Subjects will be allowed to participate in only one cohort and will receive one type of treatment, with either DM-101 or placebo, throughout the study. Cohort 1 of the study included a single dose administration. Cohorts 2 to 4 include repeat dose administration.

Table 2 and 8 describes the type of dosing with DM-101 scheduled to be administered in each cohort of study participants.

The study was started with cohorts 1 and 2, and will now proceed to cohorts 3 and 4 after a substantial protocol amendment. The amended protocol version 2.0 will be followed for the conduct of cohorts 3 and 4. A previous protocol version (1.1) was followed for cohorts 1 and 2.

Dose escalation will be initiated only upon satisfactory review of all available safety data from the previous cohort(s) and favorable recommendation from the study's SRC.

An overall schematic of the study design is presented in Figure 1.

[figure not shown]

Figure 1. Overall Study Design Schematic

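### Cohort 4 steps from 200 ng to 300 ng with no scheduled Safety Review Committee review of its own 200 ng data

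*Protocol*

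**What the plan says.** Table 8 gives cohort 4 daily doses of 30, 50, 100, 200 and 300 ng at Visits 2 to 6. Section 3.2 allocates 6 subjects to DM-101 and 2 to placebo.

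**SRC review points.** Item 1 of the SRC's remit in Section 3.3 is "providing recommendations on the dose escalation from 100 ng to 200 ng in cohort 4 based on the safety data collected" through cohort 3 Visit 5 and cohort 4 Visit 4. Item 2 is a recommendation "on continuation of dosing of cohort 3 to Visit 6". Items 3 to 5 are a standing remit over continuation, dosing changes and safety measures. Further meetings are held as needed, and "additional meetings will be triggered by safety observations as described in Section 9". Sections 3.2 and 6.3 repeat the requirement for a favourable recommendation before the 200 ng dosing at cohort 4 Visit 5. Neither names one before Visit 6. The opening of Section 9 refers back to Section 3 for the SRC's review timepoints.

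**Scope of the review.** Section 1.2.3 says: "Dose escalation to doses above 100 ng in cohort 4 will only take place if the review of the collected safety" and tolerability data from cohort 3 Visit 5 is favourable. Section 1.4 says much the same.

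**General rules.** The synopsis says: "Dose escalation will be initiated only upon satisfactory review of all available safety data from previous dose levels and favourable recommendation" from the SRC. Section 3.1 asks for "satisfactory review of all available safety data from the previous cohort(s) and favorable recommendation". Section 12 puts SRC review between cohorts. Within a cohort it relies on safety and the Section 9 criteria.

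**The concern.** The last step of the regimen reaches its highest daily dose. By then up to 6 active subjects will have had 200 ng, the first daily dose above 100 ng under the slow schedule. Nothing in Sections 3.2, 3.3 or 6.3 requires the SRC to look at those data before 300 ng is given.

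This trial has already produced a signal below its study thresholds. In cohort 2, systemic reactions occurred in 3 of 5 participants (Section 4.1). The 4 DM-101 subjects had 50 IMP-related TEAEs, none severe and none serious (Table 7). No study stopping criterion was met. The SRC met at the principal investigator's request three days after the Covid-19 halt, saw safety signals and recommended discontinuing that regimen (Section 1.2.3).

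The protocol's reassurance from cohort 2 is about 100 ng: "Systemic allergic reactions were reported in cohort 2, but none was reported following injection of the dose of 100 ng". If mild or moderate systemic reactions cluster at 200 ng, whether the SRC meets before 300 ng depends on someone choosing to call it.

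**Working it through.** **1. Dose sequence (Table 8).** For cohort 4, 30 + 50 + 100 + 200 + 300 = 680 ng, which matches the stated cumulative dose. The step ratios are 50/30 = 1.67, 100/50 = 2.0, 200/100 = 2.0 and 300/200 = 1.5. The step in question is the smallest in ratio and the last.

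**2. What the SRC will have reviewed before 300 ng.** From cohort 3 through Visit 5, the highest dose is 100 ng. From cohort 4 through Visit 4, it is also 100 ng. From cohort 2, single injections went up to 5,000 ng, but under rapid same-day escalation. Slow-schedule data at 200 ng: none by schedule.

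**3. What would bring the SRC together after Visit 5 (Sections 3.3 and 9.1 to 9.3).**

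| Finding in cohort 4 after 200 ng | Response named in Section 9 | SRC review required? |
|---|---|---|
| Death possibly due to treatment or procedure, or one Grade 4 systemic reaction | Dosing suspended (9.1) | Yes |
| Grade 3 systemic reactions in 2 subjects of the cohort | Dosing suspended (9.1) | Yes |
| Grade 4 injection site reaction in 3 subjects of the cohort | Dosing suspended (9.1) | Yes |
| One Grade 3 systemic or injection site reaction | That subject returns to the previous tolerated daily dose (9.3) | Not settled: 3.3 points to Section 9 as a whole, but only 9.1 sets out an SRC step |
| Any number of Grade 1 or 2 systemic reactions | None named; the investigator may stop a subject at discretion (9.2) | No; only an as-needed meeting |

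The conclusion rests on the last row and does not depend on how the fourth row is read. The sentinel hold at Visit 6 does not change it, because that hold is tied to the stopping and treatment discontinuation criteria.

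**4. Time available for a review.** Visit 5 is on Day 42 and Visit 6 on Day 56, each with a window of 2 days either way (Table 11). Dosing runs in three groups (the sentinel pair, two further subjects, the rest) with at least 22 h between groups. Each subject has two injections at least 30 min apart and a telephone call at 24 h.

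- Time from the first Visit 5 injection to the last 24 h call: 3 × 0.5 h + 2 × 22 h + 24 h = 69.5 h, or 2.9 days.
- Nominal interval: 56 − 42 = 14 days; 14 − 2.9 = 11.1 days before the sentinel pair's Visit 6.
- Adverse windows (Visit 5 two days late, Visit 6 two days early): 54 − 44 = 10 days; 10 − 2.9 = 7.1 days.

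The 22 h and 30 min gaps are minimums, so 11.1 and 7.1 days are upper limits for their scenarios.

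**5. What the review could show.** If 6 active subjects receive 200 ng and none has a Grade 3 systemic reaction, the one-sided 95% upper bound on the per-subject rate is 1 − 0.05^(1/6) = 0.393. A clean result excludes only rates above 39%.

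**The case against.** The best case for the plan is that one review is a consistent choice. Sections 1.2.3 and 1.4 clear all doses above 100 ng on it, and Section 12 has a separate rule for escalation within a cohort. The step is 1.5-fold and no injection exceeds 100 ng. One active sentinel receives 300 ng first, and Section 9.3 holds back individuals. Grade 2 to 5 systemic reactions reach the Sponsor within 24 h (Section 8.4.1). The SRC includes the principal investigator, the Medical Monitor and Sponsor representatives, so its members would know of such events. In cohort 2 the first two injections, about 30 min apart, total 100 + 250 = 350 ng, so the SRC already holds same-day data above 300 ng. Ad hoc review worked in 2020. A review of six subjects has little statistical power.

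Most of this stands, and it keeps the point modest. It does not supply a scheduled review of 200 ng data under the slow schedule. The cohort 2 data come from the regimen that the SRC recommended discontinuing. The value of the review lies in weighing a pattern of events, not in bounding a rate.

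Four stronger readings are tempting and should not be drawn:

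- **That the protocol contradicts itself on whether this review is required.** The synopsis phrase about dose levels follows a sentence on moving from cohort to cohort. Read literally, it would also demand SRC decisions at 30 to 50 ng and 50 to 100 ng, which no operational section contains.
- **That the visit numbering obscures which dose the review covers.** One sentence in Section 1.2.3 puts 200 ng at Visit 4 and 300 ng at Visit 5. That is a slip. Sections 3.2 and 3.3 define the review by both dose and visit, and Section 1.2.3 itself also gives the sequence as in Table 8.
- **That a repeat 100 ng dose in cohort 3 is held to a stricter rule than an escalation in cohort 4.** The cohort 3 Visit 6 item reads naturally as a decision of the same meeting, which has cohort 3 Visit 5 data before it.
- **That subjects at 300 ng are unprotected.** The safeguards above show otherwise.

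**Conclusion.** The concern holds in a limited form. Up to 6 active subjects (fewer if Section 9.3 holds any back) move from 200 to 300 ng with no SRC review of 200 ng data scheduled in Sections 3.2, 3.3 or 6.3. A pattern of Grade 1 or 2 systemic reactions at 200 ng would prompt a meeting only at someone's discretion. This is a worthwhile and cheap improvement to subject safety. It is not a failure of the existing safeguards.

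It rests on four assumptions:

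- The claim concerns the protocol text. The separate SRC Instructions and Figure 1 are not available and might add a meeting.
- The protocol describes its revised design as version 2.0, while the SAP cites version 3.1. If the text reviewed is not version 3.1, the sponsor should check whether that version already adds the review.
- The cohort 2 experience was assessed against version 1.1 stopping criteria, so it illustrates how a signal can fall below study thresholds. It does not test the present Section 9.
- The time estimate takes both visit windows as counted from Visit 2, as in Table 11.

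**What to change.** In Sections 3.2, 3.3 and 6.3, require a favourable SRC recommendation, based on a blinded review of cohort 4 Visit 5 (200 ng) safety data, before any cohort 4 Visit 6 (300 ng) dosing.

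The cost is one extra meeting of the existing committee between Visits 5 and 6, a possible short delay of Visit 6, and inclusion in a protocol amendment. Under Section 11.4 that amendment would probably be substantial and need Ethics Committee and Competent Authority approval. No subjects, visits or assessments are added.

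As editorial tidying in the same amendment, align the synopsis and Sections 1.2.3, 1.4 and 3.1 with this review point, and correct the sentence in Section 1.2.3 to 200 ng at Visit 5 and 300 ng at Visit 6. If the sponsor keeps the single review, that visit correction is still due.

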## 4. STUDY SUBJECTS

### 4.1. Number of Subjects

An adequate number of subjects, with documented birch pollen allergy, will be enrolled in the study, such that up to 27 subjects will be randomized to receive treatment with IMP in the scheduled 4 cohorts of participants. In particular, in:

*Cohort 1:* 6 subjects were randomized in a ratio of 2:1 to receive single doses of DM-101 or placebo.

*Cohort 2:* 5 subjects were randomized to receive repeated doses of DM-101 or placebo before the temporary halt of the study. Because of systemic allergic reactions observed in 3 of the 5 thus far included participants on Day 1 of Visit 2, the SRC did not recommend re-start of dosing in cohort 2 without a substantial protocol amendment. Four of the 5 enrolled subjects had received DM-101 on Visit 2 and one subject had received placebo injections.

*Cohorts 3 and 4:* 8 subjects per cohort to be randomized in a ratio of 3:1 to receive repeated doses of DM-101 or placebo.

For replacement of cohort 3 and 4 subjects who prematurely discontinue the study for reasons other than TEAE, additional subjects may be enrolled at the discretion of the Investigator, following discussion and agreement with the Sponsor.

### 4.2. Eligibility Criteria

Subjects will be eligible for inclusion in this study only if all of the following criteria apply:

#### 4.2.1. Inclusion Criteria

1. Males or females, aged 18 to 65 years inclusive.
2. Good general health, as determined by the Investigator, based on medical evaluation, including medical history, physical examination, laboratory tests and electrocardiogram (ECG).
3. A documented clinical history of birch pollen-induced allergic rhinitis or rhinoconjunctivitis with symptoms that interfere with daily activities or sleep and remain bothersome despite the use of relevant symptomatic medication, and have been present over, at least, 2 allergy seasons.
4. Bet v 1 specific serum IgE  $\geq 0.7$  kU/L (class 2), measured by ImmunoCAP®.
5. Positive SPT to birch pollen allergen, with a wheal diameter  $\geq 5$  mm (average of longest and orthogonal) greater than that produced by the negative control.
6. Body weight  $\geq 50$  kg and body mass index (BMI) within the range 18–35 kg/m^2.
7. Females are eligible to participate only if they are of:

- non-childbearing potential, defined as pre-menopausal females with documented tubal ligation or hysterectomy, or postmenopausal, defined as 12 months of spontaneous amenorrhea (in questionable cases a blood sample with levels of follicle stimulating hormone (FSH) > 40 MIU/ml and estradiol < 40 pg/ml (<147 pmol/L) is confirmatory). Females on hormone replacement therapy (HRT) and whose menopausal status is in doubt will be required to use one of the contraception methods in Section 4.3.1.1. if they wish to continue their HRT during the study. Otherwise, they must discontinue HRT to allow confirmation of post-menopausal status prior to study enrollment. For most forms of HRT, at least 2-4 weeks should elapse between the cessation of therapy and the blood draw; this interval depends on the type and dosage of HRT. Following confirmation of their post-menopausal status, they can resume the use of HRT during the study without the need to use a contraceptive method.
- child-bearing potential and have a negative serum pregnancy test result at Screening and a negative serum pregnancy test result within 10 days prior to the first dosing visit, a negative urine pregnancy test before each subsequent dosing and agree:
- to use one of the contraception methods listed in Section 4.3.1.1. starting at least 2 weeks prior to the start of dosing to sufficiently minimize the risk of pregnancy during the treatment period of the study. Female subjects must agree to use contraception until 30 days after the last treatment administration.
- or abstains from sexual intercourse or has only same-sex partner(s), when this is her preferred and usual lifestyle.

8. Males who are sexually active with a female partner of childbearing potential must agree to use one of the contraception methods listed in Section 4.3.1.2.

9. Willing and able to provide written informed consent.

10. Willing and able to comply with the study requirements.

